6.14.12 Diabetic Ketoacidosis (DKA)

DKA is a serious, acute complication of diabetes and can be life-threatening. Subjects will be educated on the signs and symptoms of DKA and are required to call the study clinic and seek treatment should such signs and symptoms occur.

During the clinical trial period, potential DKA will be monitored by the routine measurement of urinary ketones and assessment for signs or symptoms of acidosis at every clinic visit. Clinical presentations, such as difficulty breathing, abdominal pain, nausea, vomiting, lethargy, or a fruity smell in the breath, or laboratory values that suggest clinically significant acidosis should be documented. Treatment of DKA should be provided when appropriate.

If ongoing symptoms or signs suggest a possible DKA, the investigator should perform relevant laboratory testing while directing appropriate medical care for the subject. If DKA is suspected, regardless of the blood glucose level, the following assessments should be done immediately: physical exam and serum glucose, bicarbonate, electrolytes, and serum ketones measured STAT at a local laboratory. If ketoacidosis is likely, investigational product administration should be discontinued and immediate appropriate medical therapy, including insulin, should be initiated. A glucose infusion may be provided if necessary to avoid hypoglycemia during insulin therapy. Insulin treatment should continue until resolution of the ketoacidosis and stabilization of the subject's clinical condition. Investigational product administration may be resumed following stabilization of the subject's condition. Investigator should collect the data necessary for the completion of the DKA CRF.

If symptoms suggestive of DKA may have occurred but are not ongoing, investigator should review available data in order to complete the DKA CRF. The investigator may also perform laboratory assessment using local resources if necessary for clinical care.

6.14.13 Major Adverse Cardiovascular Event (MACE)

Evaluation of MACE will be undertaken across the development program for bexagliflozin. All MACE reports should also be captured as SAEs and every effort will be made to ensure that events recorded as MACE are coded in a similar manner within the safety database. The SAE listing will also be reviewed periodically by the CEC members to identify potential MACE that may not have been reported by the site investigators. All subjects will be followed by investigators for MACE for the duration of the study even if study medication has been permanently withdrawn.

The independent CEC will receive and adjudicate the following events.

- All deaths
- Suspected non-fatal myocardial infarction (MI)
- Suspected hospitalization for unstable angina (HUA)
- Suspected transient ischemic attack (TIA) and stroke
- Suspected hospitalization for heart failure (HF)
- Reported coronary revascularization procedure

6.14.14 Amputation

Amputation and related adverse events will be recorded in a case report form. During each study visit, the investigator should query the subject for any amputation and related adverse events and procedures. Investigators are reminded to counsel appropriate foot care to avoid cuts or sores and to treat even minor cuts or sores to prevent infection and ulceration. Patients who have had a previous amputation should be closely monitored. Special attention may be appropriate for patients who are also receiving thiazide diuretics as these have been shown to increase the risk of amputation in diabetics.

6.15 Concomitant Medication Assessments

A concomitant medication is any medication that the subject has been taking prior to enrollment and that the subject is expected to continue to take for some portion of the trial, as well as any medication other than the investigational product that the subject takes during the course of the trial.

The medications or treatment for controlling hypoglycemia must be recorded as concomitant medications in the CRF. Any medication given to treat hyperglycemia and continued for more than 2 weeks is considered a rescue therapy and should be recorded in the concomitant medication log.

Changes from baseline anti-hypertensive and anti-hyperlipidemia therapies and their rationale must be recorded in the CRF.

All prescription and over-the-counter medications, including vitamins and herbal supplements, that subjects receive during the trial must be documented on the CRF. This documentation should continue until the subjects complete the study.

Concomitant medications will be coded using the World Health Organization Drug Dictionary (WHO-DD). A table of concomitant medications based on the anatomic therapeutic chemical classification (ATC) and preferred name will be produced. A listing of concomitant medications will include all medications taken by any subjects during the course of the study.

6.16 Healthy-related Quality of Life Assessment

EQ-5D-3L is a multi-attribute utility instrument for measuring preferences associated with an individual's health state. The instrument includes a visual analog scale and a descriptive system with 5 dimensions (mobility, self-care, usual activity, pain/discomfort, anxiety/depression), each of which has 3 levels (no problem, some problem, extreme problem).

Enrolled subjects will complete the EQ-5D-3L questionnaire independently at clinic Visits V6, V11, V14 and V17. EQ-5D-3L should be completed prior to other scheduled procedures at those visits.

6.17 Removal of Subjects from the Trial or Discontinuation of Investigational Product Administration

The investigator must emphasize to potential subjects the importance of continued participation for the full duration of the trial during the informed consent process. Potential subjects should be informed that the trial procedures will allow additional medications to control hyperglycemia or other adverse conditions. It is also important to emphasize that missing data and missed visits could affect the entire trial. If subjects are dissatisfied with the conduct of the trial but have not withdrawn, the investigator should make an effort to address their concerns and retain them in the trial if possible. In doing so, investigators must be careful that the efforts do not cross over into coercion. Investigators should encourage a subject to remain in the study even if the investigational product administration is stopped so that safety information can be collected.

Participation in a clinical trial is voluntary. A subject can withdraw from the study at any time. The sponsor may terminate the study for medical or administrative reasons. An investigator may decline to participate in the conduct of the study if either the investigator or the Institutional Review Board (IRB)/Independent Ethics Committee (IEC) determines that, based on good medical judgment, immediate cessation is appropriate for subject safety. If a decision is made to withdraw a subject from the study, no further investigational product should be administered. Even if the subject discontinues study medication, every attempt should be made to complete all required study evaluations and procedures. Reasons for all withdrawals should be recorded on the CRF. Examples of reasons for withdrawal include:

1. A protocol violation has occurred,
2. A serious or intolerable adverse event has occurred,
3. A clinically significant change in a laboratory parameter has occurred,
4. The sponsor or investigator terminates the study, or
5. The patient requests to be withdrawn from the study.

Subjects who do not complete the study but who have received investigational product should have a follow-up examination, including a physical examination, vital signs, ECG and clinical laboratory tests according to [Section 7.6](#).

Subjects who withdraw from the study will not be replaced.

6.18 Appropriateness of Measurements

The percentage of HbA1c is a widely used measure of chronic glycemia, reflecting average blood glucose levels over a 2- to 3-month period of time. It is an accepted surrogate marker of risk of microvascular complications and is widely used as a measurement for the adequacy of glycemic management. Other study procedures and measurements in this protocol are widely used and generally recognized as reliable, accurate, and relevant for subjects with T2DM.

7 STUDY ACTIVITIES

The study activities at each clinic visit listed below are presented in [Appendix 1](#). The required laboratory tests scheduled at each visit are listed in [Appendix 2](#). Detailed study procedures are described in [Section 6](#).

A visit window of ± 3 days is allowed for all visits except Visit V6. Visit V6 is the day of randomization and is the basis for all subsequent visit windows.

7.1 Screening Period

7.1.1 Visit V1 (3 days to 3 weeks for metformin-only group and up to 9 weeks for metformin-and-OHA group before run-in period)

The screening can be performed from 3 days to 3 weeks before the start of the wash-out period for subjects who are metformin-and-OHA treated and 3 days to 3 weeks before the start of the run-in period for subjects who are metformin-only treated. At the screening visit, the staff at the investigational site will:

- Explain the content of the informed consent materials to the subject and collect signed informed consent
- Evaluate inclusion and exclusion criteria based on the information collected at the screening visit. Verify compliant fasting status as described in [Section 6.9.2.1](#).
- Obtain medical history and demographic information
- Perform an abbreviated physical examination and record body weight and height
- Measure vital signs, including blood pressures and heart rate
- Perform a 12-lead ECG measurement
- Draw blood if a minimum 10 h fast has been completed by the subject as described in [Section 6.9.2.1](#). The specific laboratory tests scheduled for this visit are listed in [Appendix 2](#).
- Collect a clean-catch, mid-stream urine sample

7.2 Wash-out and Run-in Period (Up to 8 weeks prior to randomization)

The wash-out and run-in period is required for any enrolled subject who is taking metformin and one additional OHA. Eligible subjects who are taking metformin only will enter the run-in period directly.

7.2.1 Wash-out Period (Visits V2 and V3)

Two visits will be conducted during the wash-out period. V2 is an on-site clinic visit. At V3 each subject will be evaluated by the investigator or study staff via a phone interview.

7.2.1.1 Visit V2 (8 weeks prior to randomization)

- Evaluate inclusion and exclusion criteria based on the information collected at the screening visit. Verify compliant fasting status as described in [Section 6.9.2.1](#).
- Counsel subject on appropriate diet and exercise (for subjects who are metformin-and-OHA treated)
- Dispense glucometer and instruct subject in SMBG determination and recording (for subjects who are metformin-and-OHA treated)
- Start wash-out and discontinue the non-metformin OHA
- Assess adverse events and potential DKA
- Record pre-treatment medications

7.2.1.2 Visit V3 (6 weeks prior to randomization, off-site phone visit)

- Review SMBG and glycemic control record
- Assess adverse events and potential DKA
- Record pre-treatment medications

7.2.2 Run-in Period

7.2.2.1 Visit V4 (2 weeks prior to randomization)

- Counsel subject on appropriate diet and exercise (for subjects who receive metformin only and do not need a washout)
- Dispense glucometer and instruct subject in SMBG determination and recording (for subjects who receive metformin-only)
- Review SMBG and glycemic control record (for subjects who receive metformin + 1 OHA)
- Dispense run-in kits for run-in period
- Measure vital signs, including blood pressures and heart rate
- Assess adverse events and potential DKA
- Record pre-treatment medications

7.2.2.2 Visit V5 (3 to 5 days prior to randomization)

- Evaluate inclusion and exclusion criteria based on the information collected at the screening visit. Verify compliant fasting status as described in [Section 6.9.2.1](#).
- Perform a complete physical examination and record body weight
- Review SMBG and glycemic control record
- Measure vital signs, including blood pressures and heart rate
- Perform a 12-lead ECG measurement
- Draw blood if a minimum 10 h fast has been completed by the subject as described in [Section 6.9.2.1](#). The specific laboratory tests scheduled for this visit are listed in [Appendix 2](#).
- Collect a clean-catch, mid-stream urine sample
- Assess adverse events and potential DKA
- Record pre-treatment medications

7.3 Treatment Period (Day 1 to Week 96)

At the end of the run-in period, subjects who have successfully completed run-in period and continue to meet the inclusion/exclusion criteria will be randomized and enter the treatment period.

7.3.1 Visit V6 (Day 1 of Week 1)

Visit V6, day of randomization, must be conducted after the HbA1c value from the sample of Visit V5 is available for eligibility confirmation.

- Complete EQ-5D-3L questionnaire
- Review SMBG and glycemic control record
- Collect used run-in medications and dispense investigational products based on randomization
- Assess adverse events and potential DKA
- Record concomitant medications

7.3.2 Visit V7 (Week 2)

- Review SMBG and glycemic control record
- Measure vital signs, including blood pressures and heart rate
- Collect used study medication, if applicable, and dispense glimepiride based on up-titration criteria assessment
- Assess adverse events and potential DKA
- Record concomitant medications

7.3.3 Visit V8 (Week 4)

- Review SMBG and glycemic control record
- Measure vital signs, including blood pressures and heart rate
- Collect used study medication, if applicable, and dispense glimepiride based on up-titration criteria assessment
- Assess adverse events and potential DKA
- Record concomitant medications

7.3.4 Visit V9 (Week 6)

- Perform an abbreviated physical examination and record body weight
- Review SMBG and glycemic control record
- Measure vital signs, including blood pressures and heart rate
- Collect used study medication, if applicable, and dispense glimepiride based on up-titration criteria assessment
- Draw blood if a minimum 10 h fast has been completed by the subject as described in [Section 6.9.2.1](#). The specific laboratory tests scheduled for this visit are listed in [Appendix 2](#).

- Collect a clean-catch, mid-stream urine sample
- Assess adverse events and potential DKA
- Record concomitant medications

7.3.5 Visit V10 (Week 12)

- Review SMBG and glycemic control record
- Record body weight
- Measure vital signs, including blood pressures and heart rate
- Collect used study medications and dispense investigational products
- Draw blood if a minimum 10 h fast has been completed by the subject as described in [Section 6.9.2.1](#). The specific laboratory tests scheduled for this visit are listed in [Appendix 2](#).
- Collect a clean-catch, mid-stream urine sample
- Assess adverse events and potential DKA
- Record concomitant medications

7.3.6 Visit V11 (Week 24)

- Complete EQ-5D-3L questionnaire
- Perform an abbreviated physical examination and record body weight
- Review SMBG and glycemic control record
- Measure vital signs, including blood pressures and heart rate
- Perform a 12-lead ECG measurement
- Collect used study medications and dispense investigational products
- Draw blood if a minimum 10 h fast has been completed by the subject as described in [Section 6.9.2.1](#). The specific laboratory tests scheduled for this visit are listed in [Appendix 2](#).
- Collect a clean-catch, mid-stream urine sample
- Assess adverse events and potential DKA
- Record concomitant medications

7.3.7 Visit V12 (Week 36)

- Perform an abbreviated physical examination and record body weight
- Review SMBG and glycemic control record
- Measure vital signs, including blood pressures and heart rate
- Collect used study medications and dispense investigational products
- Draw blood if a minimum 10 h fast has been completed by the subject as described in [Section 6.9.2.1](#). The specific laboratory tests scheduled for this visit are listed in [Appendix 2](#).
- Collect a clean-catch, mid-stream urine sample
- Assess adverse events and potential DKA
- Record concomitant medications

7.3.8 Visit V13 (Week 48)

- Perform an abbreviated examination and record body weight
- Review SMBG and glycemic control record
- Measure vital signs, including blood pressures and heart rate
- Collect used study medications and dispense investigational products
- Draw blood if a minimum 10 h fast has been completed by the subject as described in [Section 6.9.2.1](#). The specific laboratory tests scheduled for this visit are listed in [Appendix 2](#).
- Collect a clean-catch, mid-stream urine sample
- Assess adverse events and potential DKA
- Record concomitant medications

7.3.9 Visit V14 (week 60)

- Complete EQ-5D-3L questionnaire
- Perform a complete physical examination and record body weight
- Review SMBG and glycemic control record
- Measure vital signs, including blood pressures and heart rate
- Perform a 12-lead ECG measurement
- Collect used study medications and dispense investigational products
- Draw blood if a minimum 10 h fast has been completed by the subject as described in [Section 6.9.2.1](#). The specific laboratory tests scheduled for this visit are listed in [Appendix 2](#).
- Collect a clean-catch, mid-stream urine sample
- Assess adverse events and potential DKA
- Record concomitant medications

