3.3.2 Treatment Period

The double-blind treatment period will start at randomization and last 96 weeks. A total of 420 subjects of 210 subjects per group will be randomized in a 1:1 ratio to the two groups as shown in [Table 1](#).

Table 1. Treatment Groups and Assigned Treatment

Treatment Group	Treatment
1	Bexagliflozin tablets, 20 mg, (once daily P.O.) Glimepiride capsules, placebo, (once daily P.O.)
2	Bexagliflozin tablets, placebo, (once daily P.O.) Glimepiride capsules, 2, 4 or 6 mg, (once daily P.O.)

Randomization will be stratified by HbA1c at Visit V5 ($\leq 8.5\%$ vs. $> 8.5\%$), treatment background (metformin-only vs. metformin-and-OHA), and baseline estimated glomerular filtration rate (eGFR) at screening visit (V1) ($eGFR \geq 90$ vs. < 90 and ≥ 60 mL/min/1.73 m²). At the start of the treatment period, each subject will be provided with bexagliflozin tablets, glimepiride capsules, dosing instructions, and a glycemic control diary in which to record SMBG measurements. Symptoms and blood sugars related to the occurrence of hyperglycemia, hypoglycemic events or symptoms that may suggest ketoacidosis will be recorded. Bexagliflozin tablets, 20 mg or placebo, will be orally administered once daily prior to the first meal; glimepiride capsules, 2, 4, or 6 mg or placebo, will be taken once daily with the first meal. Background medication metformin shall be taken at an unchanged dose and frequency taken at screening throughout the entire study.

Each subject will be instructed to return to the clinic at weeks 0, 2, 4, 6, 12, 24, 36, 48, 60, 72, 84 (off-site phone visit) and 96 for efficacy assessment and safety monitoring, including review of adverse events and concomitant medication, vital signs, ECG, physical examination, and blood and urine specimen collections. On the day of a clinic visit at which blood samples are scheduled to be collected, approximately 10 hours (h) fasting must be confirmed prior to blood draw. On the day of the scheduled clinic visits at which there is fasting and blood is to be drawn, administration of bexagliflozin shall be withheld until after blood is drawn and taken with water at the clinic or home prior to the first meal; glimepiride shall be withheld and taken with the first meal of the day.

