3.3.3.2 Treatment Period

During the treatment period, subjects will be advised to continue daily, fasting SMBG measurements. Subjects should contact the clinic if any fasting SMBG is ≥ 270 mg/dL (15 mmol/L) from week baseline to week 6, ≥ 240 mg/dL (13.3 mmol/L) after week 6 to week 12, or ≥ 200 mg/dL (11.1 mmol/L) after week 12. Blood glucose values collected via SMBG will be evaluated at study visits by the investigator. In addition, hyperglycemia will be monitored by FPG at scheduled visits.

If hyperglycemia is identified through SMBG or FPG measurements, the investigator will determine whether the subject has fasted for a minimum of 10 h prior to the morning blood draw to ensure that the SMBG or FPG value is truly a fasting sample. If proper fasting has not occurred, the subject will be asked to return for a repeat blood test within a week.

During the treatment period, hyperglycemia should be managed first with diet and exercise counseling. If hyperglycemia continues after diet and exercise counseling, the investigator should intensify medical therapy if it is necessary for the well-being of the subject. Options for intensification of medical therapy will vary during the study, including up-titration of glimepiride dose (weeks 0-6) and addition of rescue medication (see below, *Intensification of Medical Therapy for Hyperglycemia*).

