5.9 Packaging and Labeling

Investigational products will be provided to the pharmacist or designated site personnel in high-density polyethylene (HDPE) bottles of 90 tablets enclosed with a child-resistant cap. A bottle of 15 bexagliflozin tablets, placebo, and a bottle of 15 glimepiride capsules, placebo, will be provided for the 2-week run-in portion of the study. All investigational product supplies will be prepared and labeled according to the requirements of local laws and regulations. The pharmacist or designated site personnel will dispense the investigational products for each subject according to randomization assignment.

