6.9.2 Sample Collection, Storage, and Shipping

6.9.2.1 Hematology, Blood Chemistry, Serum Lipids, and Glycemic Control Assessments

Blood samples for hematology, chemistry, serum lipids and glycemic control assessments will be collected. Subjects will be in a seated or supine position during blood collection. Samples will be collected at the time points indicated in the schedule of events in [Appendix 1](#) and [Appendix 2](#).

The study staff will contact each subject prior to a scheduled clinic visit to confirm the time of the visit and to remind the subject of proper fasting practice. A subject must be queried to assess compliance with an approximately 10 h fast prior to blood draw to ensure the FPG and triglycerides values can be accurately determined. If a subject has not fasted for approximately 10 h, the subject must return as soon as can be arranged (within 1 week) to provide a specimen after proper fasting.

Low-density lipoprotein-cholesterol (LDL-C) will be calculated by the Friedewald equation. If triglycerides are > 400 mg/dL, the calculated LDL-C value is invalid by this equation and will be set as missing. Direct LDL-C will be determined in subjects whose triglycerides are > 350 mg/dL at screening visit. All subsequent LDL-C of these subjects will be determined by the same direct LDL-C measurements only.

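### HbA1c at the scheduled visits is tied to a 10 h fast that it does not need, so a non-fasted subject's value is deferred to a return visit and lost if the subject does not come back

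*Protocol*

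**What the plan says.** The week-60 visit list (Protocol 7.3.9) instructs the site: "Draw blood if a minimum 10 h fast has been completed by the subject", with a cross-reference to Section 6.9.2.1. The lists for V1, V5, V9 to V13, V15, V17 and V18 use the same condition. Protocol 3.3.2 adds that "approximately 10 hours (h) fasting must be confirmed prior to blood draw". Protocol Appendix 2 schedules HbA1c at V1, V5, V10 to V15, V17 and V18, but not at V9.

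Protocol 6.9.2.1 says that subjects are asked about fasting "to ensure the FPG and triglycerides values can be accurately determined". If the fast was not kept, "the subject must return as soon as can be arranged (within 1 week) to provide a specimen after proper fasting". SAP 3.11 and 9.4 repeat this return rule. Protocol 6.18 describes HbA1c as reflecting average glucose over 2 to 3 months.

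Other parts of the protocol are not aligned with the visit lists:
- The sample required before rescue medication, taken to obtain a final HbA1c (3.3.3.3), has no fasting condition.
- The glycemic-control tests for subjects who withdraw consent (7.6) have none either, whereas V18 (7.4.1), which also covers withdrawal of consent, does.
- The visit lists make 10 h a minimum, while 3.3.2 and 6.9.2.1 ask for approximately 10 h.

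**The concern.** Change in HbA1c at week 60 is the primary endpoint. Nothing in the protocol tells a site to take HbA1c from a non-fasted subject at a scheduled visit, and nothing in it gives a reason to withhold the sample. As written, the value depends on a second trip that the test does not need.

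Two groups are the most exposed. The first is subjects at an early-termination V18, some of whom are withdrawing consent and are the least likely to return. SAP 6.4 maps early-termination values to analysis visits, and SAP 8.1 uses all post-baseline values up to week 60, so such a value can matter even outside the week-60 window. The second is subjects who have stopped treatment but attend week 60. Their values are the basis of the retrieved-dropout imputation in SAP 8.1.1, which is run only if at least 3% of each arm, about 6 subjects, completed the week-60 visit off treatment.

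Both documents commit to minimising missing data through study conduct (Protocol 9.5.3, SAP 8.1.2). This wording works against that.

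**Working it through.** **1. The plan's sample size.** Inputs from Protocol 9.2: margin 0.35, SD 1.0, one-sided alpha 0.025, power 90%, dropout 18%. The documents state no true difference; zero is assumed.

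n per arm = 2 × [(1.960 + 1.282) × 1.0 / 0.35]² = 171.55, rounded up to 172. With 18% dropout, 172 / 0.82 = 209.8, rounded up to 210. Both planned figures reproduce.

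**2. Does a late redraw still count as week 60?** The protocol window is given by "A visit window of ± 3 days is allowed for all visits except Visit V6". The week-60 target is Day 420.
- Latest in-window V14: 420 + 3 = Day 423.
- Latest redraw under the 1-week rule: 423 + 7 = Day 430.
- SAP Table 3 window for week 60: Day 378 to Day 461, with unscheduled visits mapped.
- Distance to the upper limit: 461 − 430 = 31 days.

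A redraw can miss the protocol visit window but stays in the week-60 analysis window. The loss is therefore confined to subjects who do not return.

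**3. Size of the loss.** Let x be the share of otherwise evaluable subjects who arrive non-fasted at week 60 and never return. The documents give no value for x, so the range is an assumption. Evaluable n = 210 × 0.82 × (1 − x). Power = Φ(0.35 / √(2/n) − 1.960).

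| x | n per arm | power |
|---|---|---|
| 0 | 172.2 | 90.1% |
| 1% | 170.5 | 89.8% |
| 2% | 168.8 | 89.5% |
| 3% | 167.0 | 89.2% |
| 5% | 163.6 | 88.6% |
| 10% | 155.0 | 86.9% |

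At 1-3% the loss is 1.7 to 5.2 values per arm and 0.3 to 0.9 points of power. This is a complete-case calculation. The planned MMRM or multiple imputation also uses earlier HbA1c values, so it overstates the loss of information.

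**4. The retrieved-dropout threshold.** 3% of 210 is 6.3 per arm. If an arm has only 6 or 7 off-treatment subjects at week 60, losing one or two of their values could leave the imputation too thin. SAP 8.1.1 words the threshold as visits completed but the fallback to MMRM as too few values available. A subject who attends without a blood draw could thus count towards the threshold and contribute nothing. The documents do not say how many such subjects are expected.

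**The case against.** The strongest reply is that the return rule is mandatory and sits in the very section the visit lists cite. Protocol 6.9.2.1 also has staff contact each subject before the visit with a fasting reminder. A reader might infer from the conditional wording that a non-fasted subject gives no primary-endpoint value at all. The documents do not support that: the value is deferred, and the SAP window accepts it.

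The texts can also be read more leniently. Section 6.9.2.1 does not itself forbid drawing at the visit. Section 3.3.3.2, on hyperglycemia found without a proper fast, says "the subject will be asked to return for a repeat blood test within a week", which suggests that some non-fasted blood is drawn. Section 7.6 may also secure a last HbA1c from a subject withdrawing consent. These points stand, but they show that the sections need reconciling, not that the HbA1c is protected.

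For completers, V18 is at week 98 and has no bearing on the primary endpoint. The SAP's tipping-point analysis (8.1.2) already addresses missing HbA1c. That the loss would be non-random is plausible but not shown.

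A further stronger reading concerns V5. The run-in supply is limited: "A bottle of 15 bexagliflozin tablets, placebo, and a bottle of 15 glimepiride capsules, placebo, will be provided for the 2-week run-in portion". A reader might infer that a 7-day redraw would exhaust it and bar the subject from randomisation for missed doses. That requires the full week's delay, the usual gap before V6 and no resupply. It also treats doses never supplied as doses omitted, which the documents do not say.

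**Conclusion.** The point holds as an avoidable weakness of low severity. HbA1c is conditional on a fast that the protocol justifies only for FPG and triglycerides, and no text secures the sample at the visit. If every non-fasted subject returns, nothing is lost. If 1-3% of evaluable subjects did not (an assumption), power would fall from about 90.1% to about 89.8-89.2%, at a true difference of zero and the plan's SD.

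That power loss would not by itself justify an amendment. The case rests on how easily the loss can be prevented and on where it would fall: early-termination visits, and the few off-treatment week-60 values on which the SAP's primary method depends. It does not extend to all blood draws, since the pre-rescue sample and the Section 7.6 tests carry no fasting condition.

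**What to change.** In Protocol 7.1.1 to 7.4.1, replace the conditional draw with wording to this effect: HbA1c and the other tests that do not need fasting are drawn at the scheduled visit whatever the fasting status; fasting status is recorded; a non-fasted subject is recalled within 1 week for FPG and lipids only. Align Section 3.3.2 and the return rule in Protocol 6.9.2.1, SAP 3.11 and SAP 9.4.

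Two safeguards are needed:
- Glucose is part of the chemistry panel (Protocol Table 3), so a result from a non-fasted draw should be flagged as non-fasting.
- V5 is only 3 to 5 days before randomisation, so a recall within 1 week could fall after dosing starts. SAP 6.2.1 takes baseline on or before the first double-blind dose. Without a V5 value, baseline FPG would revert to screening, which precedes wash-out in metformin-and-OHA subjects. The V5 recall for FPG and lipids should therefore be completed before the first double-blind dose.

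Also reconcile V18 with Section 7.6, and the minimum 10 h with the approximate 10 h.

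The cost is a wording amendment and an occasional second small blood sample at a recall visit that is already required.
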